Acknowledging the benefits of combined electrotherapy and KOA as a progressive and degenerative condition with unlikely regression or restoration of damaged structures, the study aims to investigate the effects of stimulation assisted activities to delay the disease progression and muscle atrophy in those with KOA. Thus, the purpose of this research is to investigate if stimulation assisted (NMES and FES) activities can combat disuse atrophy for individuals diagnosed with KOA. This study will use a home-based medical device (Cionic Neural Sleeve NS-100, K213622, CIONIC, San Francisco, CA) to administer electrical stimulation and measure its effect on outcomes that include quadriceps strength, perceived functional capacity, pain, and walking performance.

Significance

Adults with KOA spend most of their day engaging in sedentary behavior and report worse physical function⁸, which may lead to progression of the condition, increased functional dependence and decreased quality of life²². Existing literature shows that NMES assisted exercise may counter disuse atrophy in sedentary individuals²³, but because there has been minimal research investigating the effects of FES in the KOA community, exploration of this study is warranted.

Figure 1: Cionic Neural Sleeve system

Note: Left: Cionic Neural Sleeve showing the configuration of the FES and electromyographic (EMG) electrode arrays. Center: Cionic mobile application interface for setting FES parameters (frequency, pulse width, intensity) and current field steering. Right: Cionic Neural Sleeve on body.

Research Objectives

1. Analyze the effects of electrical stimulation assisted interventions versus a conventional exercise program on muscle strength, perceived function, and pain in KOA.
2. Compare the effects of unassisted walking and stimulation assisted walking on walking performance in KOA.
3. Measure the compliance of electrical stimulation assisted interventions to a conventional exercise program on the effects of pain and perceived function in KOA.

Hypotheses

It was hypothesized that combined electrotherapy groups will show larger muscle mass and strength improvements; improved gait kinematics, pain and perceived function; and a high compliance to the assigned program compared to the unstimulated group.

Specific Aims

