The study will be explained to the participants and written informed consent will be obtained before the initial lab visit. Physical measurements, performance tests, and questionnaire responses will be collected at three lab visits: initial, study midpoint (6 weeks), and end of study (12 weeks). Physical measurements will include height, weight, and thigh circumference of the impacted leg. If subjects report bilateral compromised legs, the most impacted/painful leg will be measured. Participants will be asked to complete four performance tests (maximal voluntary isometric contraction of the quadriceps, Five Times Sit to Stand Test (FTSST), 10-meter Walk Test (10mWT), and the 6-Minute Walk Test (6MWT)) and three questionnaires (Western Ontario/McMaster Universities Osteoarthritis Index physical function (WOMAC-PF) subscale, WOMAC-pain, and the Short Form-36). Order of the tasks at the lab visits are as follows: maximal voluntary isometric contraction of the quadriceps, FTSST, 10mWT, WOMAC-PF, 10mWT, WOMAC-pain, 6MWT, Short Form-36, and 6MWT. Instruction will be provided to the participants before beginning a new task, and the researchers will periodically gauge the subjects for a need for a break and understanding of the task. For the walking tests, subjects will be fitted with the electrical stimulation system to collect EMG/kinematic data, and depending on the subject's group assignment, stimulation may or may not be enabled. All subjects will be provided with and instructed to wear the electrical stimulation system for the subsequent 12 weeks. All subjects will be taught how to navigate the supporting app and receive a user manual on how to operate/care for the system. Subjects assigned to receive stimulation will be taught how to adjust parameters of the device using the supporting app. All participants will receive a handout explaining the exercise, and a calendar for the exercise and walking program (Appendix

B). Subjects will be informed to perform the exercise and walking program in an area free from obstacles. Lab visits may be up to 90 minutes in duration.

Exercise and Walking Program

The participants will wear the device during the 12-week exercise and walking program. This may range from 1 minute to 35 minutes per day (Appendix B).

Exercise Program

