If participants have questions during the study, they may call, text ([contact]), or email the primary investigator (PI) directly ([contact]) at any time. If a participant loses or damages the system (Control Unit or the Cionic Neural Sleeve), the equipment will be replaced via next day freight or by in-person pickup from the lab site. Broken or damaged equipment may be returned to the lab in person or CIONIC will mail a return shipping label and box. Under no circumstances will the participant be financially responsible for any damaged devices or associated shipping costs. If a participant chooses to withdraw from the study, they may return the equipment to the lab in person or CIONIC will mail them a return shipping label and box. Participants who lose or irreparably damage two sleeves or Control Units may be asked to withdraw from the study early but will be compensated for their time.

Primary Outcome Measures**Quadriceps Strength**

Quadriceps strength, as measured by maximal voluntary isometric contraction (N), will be assessed using a handheld dynamometer according to a testing protocol²⁴ for both limbs. To assess maximal voluntary isometric contraction of the quadriceps, participants will be seated with the back erect and legs hanging over the edge of the treatment table. The researchers will visually ensure that the subjects are sitting upright before administering the test, but if the subjects are not seated upright, the researchers may give them a tactile cue for posture if needed. With the handheld dynamometer placed distally on the affected leg with the knee in 90 degrees flexion, participants will push against the dynamometer for 5 seconds. Subjects will get two

warm-up trials separated by a 1-minute rest period. The first warm up will be at 50% maximal effort, and second trial at 70% maximal effort, with contractions to be held for 5 seconds. Subjects will then perform 3 repetitions of maximal effort, separated by two minutes of rest between each. The test will be repeated on the other leg. The average of the 3 repetitions will be recorded as the subjects' 1 repetition maximum, the gold standard for evaluating dynamic strength in non-laboratory conditions²⁵.

Perceived Functional Capacity

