Walking endurance (m) will be measured using the 6MWT using the same walkway utilized for the 10mWT. Participants will wear the Cionic Neural Sleeve during the two 6MWTs. For the 6MWT, the subject will be instructed to walk as far as possible for 6 minutes, up and down the pathway, and pivoting to turn at the end of each lap³¹. Timing will begin when the participant steps over the start line, and distance traveled will be recorded. Encouragement outlined in the guideline (Appendix C) will be given to the subjects after each minute, and participants will be instructed to stop at 6 minutes or prior, if they are unable to complete 6 minutes. Use of a walking aid and standing rests will be permitted. Normative values of people aged 40-80 years will be used as reference values³².

Secondary Measures

Adherence to Program

Adherence to the program will be measured by the usage log of the Cionic Neural Sleeve. The data collected from the Cionic Neural Sleeve worn on the affected limb/most affected limb will be recorded to monitor compliance to the program in number of repetitions and duration of walking.

Thigh Muscle Volume

Thigh muscle volume will be estimated using a measurement tape for thigh circumference and a prediction model. Thigh circumference (cm) will be measured from a point 15 cm proximal to the superior pole of the patella. The prediction model is as follows: Muscle volume (cm³)

=4226.3 – 42.5×age(year) – 955.7× gender(male=1, female=2) + 45.9×body weight(kg) + 60.0×thigh circumference(cm)³³. It was selected for this study for its correlation ($r^2 = 0.745$) to magnetic resonance imaging, the gold standard of measuring muscle volume³⁷.

Functional Ability of the Lower Limb

To measure functional ability of the lower limb, subjects will be asked to perform the FTSST. The FTSST requires participants to sit in a chair with their arms crossed over the chest and then to stand up/sit down for five times, as fast as possible³⁴. Subjects will be timed from the initial sitting position to the final standing position. Cut-off points of 10.8 and 12.8 seconds will be used as references for intermediate and poor function, respectively³⁵.

Quality of Life

The Short Form 36 (SF-36) is a generic measure of health status that measures self-reported functional health and well-being in the past four weeks in eight domains or two summary scores. Scores range from 0 to 100, with 0 representing extreme interference, and 100 representing no interference³⁶.

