1. Performing routine exercise (with or without stimulated assistance) has been shown to improve general health, strength, and pain.
2. Walking with a stimulation device may facilitate neural retraining which could result in improved motor control, pain, and walking performance. Although this has been anecdotally reported in previous studies, CIONIC hopes to establish this with clinical endpoints in this study.
3. If requested, CIONIC will provide the participant with a copy of their data, which the participant may choose to share with members of their clinical team to support their care. CIONIC is not a medically licensed company and cannot and will not provide medical advice; however, CIONIC will explain the data in more detail to the participant if requested.

Study Withdrawal

During the consent process, participants will be informed that they may withdraw from the study at any time. The study team member responsible for reviewing informed consent will confirm that they understand that they have this option. Participants will be entitled to financial compensation for each lab visit. The investigators or sponsors may stop the study or take participants out of the study at any time should they judge that it is in their best interest, if subjects experience a study-related injury, if subjects need additional or different medication/treatment, or if they do not comply with the study plan. The researchers may remove participants from the study for various administrative and medical reasons. Participants will not be compensated for lab visits that they cancel or miss.

Data Storage, Monitoring and HIPAA

This study involves the collection of data from sensors on the Cionic Neural Sleeve system, and possibly external kinematic data collection systems for validation. Data collected will not include personally identifiable information. The devices comprising the system connect wirelessly via BLE to an application running on a smartphone or iPad.

CIONIC's smartphone or iPad's camera will also record video of the lower body at the lab visits. The participant's face and voice will not be recorded. The content of the data will be uploaded to a secure server. Each set of data will be organized using a unique numerical identifier that does not include protected health information (PHI) (e.g., initials) will be stored in our Health

Insurance Portability and Accountability Act (HIPAA) compliant database with access limited to

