CIONIC employees who will administer the study. This unique identifier (date of testing and study session) will be recorded separately in a participant tracking file which will include demographic data such as gender, age, diagnosis, and duration of diagnosis. Adverse events (AEs) and protocol deviations will be recorded for each participant. This data will also be stored on a secure server.

The PI, [name], will be responsible for ensuring participants' safety on a daily basis. Data collected from this study will be reviewed on a weekly basis by the PI and sponsor for each week there are study participants. All data will be collected and stored on a secure server. There is no Data and Safety Monitoring Board for this study.

All AEs will be reviewed by the PI within one business day of occurrence. AEs determined to be Serious adverse events related to subject safety will be reported to Salus Institutional Review Board within one business day of review by the PI. AEs and unanticipated problems will be reviewed on a monthly basis in order to ensure good practice and identify any emerging issues of concern. The PI will determine whether the study should be modified based on these findings.

Quality assurance activities include following written and consistent procedures. Data collection pages will be reviewed monthly to ensure the quality of the data collection, management, and analysis.

The study sponsors recognize the requirement to adhere to HIPAA. As stated, all participant PHI will be stored in our HIPAA compliant database with access limited to CIONIC study staff.

Additionally, individual data will not be publicly disclosed. In the future, aggregate data from the study (mean, variance, demographic data) may be used to disseminate the results.

Data Storage and Contact for Future Studies

In the informed consent document, participants will indicate whether they would like their information to be saved for future studies. If they select “Yes”, their information will be saved. If they select “No,” their information will be destroyed from all databases. Study records and study data will be kept indefinitely or until users request they be deleted.

Debriefing Procedures

At the beginning of each lab visit, there will be a debriefing with the participants, where they will be informed of assessments to complete. At the end of the lab visits, subjects may provide feedback about the Cionic Neural Sleeve system.

Costs to Participants

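### Participants may be taken out of the study for non-compliance or for needing other treatment, with no provision for later assessments and no defined analysis set, so missing data may be related to outcome

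*Combined protocol and SAP*

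**What the plan says.** Under Study Withdrawal: "The investigators or sponsors may stop the study or take participants out of the study at any time". The grounds listed include the participant's best interest, study-related injury, and "if subjects need additional or different medication/treatment, or if they do not comply with the study plan". A further sentence is open-ended: "The researchers may remove participants from the study for various administrative and medical reasons". No threshold for non-compliance is given.

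On what happens afterwards, Study Removal and Device Returns deals only with equipment: "If a participant chooses to withdraw from the study, they may return the equipment to the lab in person". Lab Visits schedules assessments at baseline, 6 weeks and 12 weeks and does not mention participants who have been removed. Compensation for Participation withholds the gift card from anyone who does not complete the whole study.

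On the outcomes concerned, Overview of Study lists strength, perceived function, pain and walking performance as primary, and adherence as secondary. Sleeve usage data "will be recorded to monitor compliance to the program in number of repetitions and duration of walking", and Table 2 has adherence assessed weekly. The Hypotheses section expects the stimulated groups to show "a high compliance to the assigned program compared to the unstimulated group".

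On who sees what, Data Storage, Monitoring and HIPAA states: "Data collected from this study will be reviewed on a weekly basis by the PI and sponsor". No blinding is described, and under Lab Visits staff teach stimulated participants to set the device and enable stimulation by group.

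Data Analysis/Statistical Analysis plans paired t or Wilcoxon tests within groups, ANOVA or Kruskal-Wallis across groups, and optionally a repeated measures ANOVA. It names no analysis set, no missing-data method and no rule for added treatment.

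**The concern.** Both removal grounds touch what the trial measures. Non-compliance is the low end of the adherence outcome, so removing low compliers and analysing the rest conditions on an outcome. Needing additional or different treatment may be a sign of worse pain or function. If such participants leave and are not assessed, week-12 values are missing for reasons linked to the values themselves. The comparison then drifts from the randomised arms towards people who complied and did not need other treatment.

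Removal could differ by arm. Risk & Benefit Assessment lists discomfort from stimulation and anxiety about receiving it, and only the stimulated groups are exposed to these. Because removal is discretionary, without a threshold, and decided by people who know the assignment and review accumulating data, nothing in the plan keeps it even-handed. The loss cannot be repaired at analysis: a week-12 assessment not done is gone.

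**Working it through.** **The plan's own figures.** Appendix A gives 32 for comparing group A with group B on WOMAC function (effect size 0.71, two-sided alpha 0.05, power 80%). By the normal approximation, 2 × (1.960 + 0.842)² / 0.71² = 31.1, rounded up to 32. This is a per-group number. Participation Selection and Randomization uses 32 as the total, which is a separate matter. That section raises 32 to 45 for dropouts without giving a rate. The implied overall allowance is 1 − 32/45 = 28.9%. It covers dropout of any cause and says nothing about removals or differences between arms.

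**Model for the bias.** The documents give no removal rate and no link between removal and outcome, so all rates and correlations here are assumptions. Suppose a share q of an arm is removed, those with the highest propensity for removal leave, and that propensity correlates r with poor outcome (bivariate normal). The mean of those remaining then shifts favourably by r × m(q) SD, where m(q) = φ(z)/(1 − q) and z is the (1 − q) normal quantile.

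- m(0.10) = 0.1755/0.90 = 0.195
- m(0.20) = 0.2800/0.80 = 0.350
- m(0.289) = 0.481
- m(0.30) = 0.3477/0.70 = 0.497

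**Between arms**, with the same r in both arms, the bias is r × [m(q₁) − m(q₂)]:

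| Removed, arm 1 vs arm 2 | r = 0.3 | r = 0.7 |
|---|---|---|
| equal | 0 | 0 |
| 20% vs 10% (difference 0.155) | 0.05 SD | 0.11 SD |
| 30% vs 10% (difference 0.302) | 0.09 SD | 0.21 SD |
| 30% vs 0% (difference 0.497) | 0.15 SD | 0.35 SD |

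Equal rates protect only if r is also equal. At 20% removed in both arms, with r = 0.3 in one and 0.7 in the other, the bias is 0.350 × (0.7 − 0.3) = 0.14 SD.

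Against the planning effect of 0.71, the 30% versus 10% row is 0.09/0.71 = 13% to 0.21/0.71 = 30%. The comparison is rough, because the documents do not say which SD underlies the 0.71.

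**Within an arm.** The before/after tests take the full shift r × m(q), in SDs of change, even when every arm loses the same share. At 28.9% removed this is 0.3 × 0.481 = 0.14 to 0.7 × 0.481 = 0.34 SD.

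**Adherence.** The programme schedules 60 exercise sessions (5 per week) and 36 walking sessions (3 per week). Removal at week 3, 6 or 9 caps the log at 15, 30 or 45 exercise sessions and 9, 18 or 27 walking sessions. As an illustration, assume 15 in an arm, 11 completers at 80% adherence, and 4 removed at week 6 after adhering at 40%:

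- completers only: 80%
- all 15, each over their time on study: (11 × 0.80 + 4 × 0.40)/15 = 69%
- all 15, over the full schedule: (11 × 0.80 + 4 × 0.40 × 0.5)/15 = 64%

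The same data give 80%, 69% or 64%, and the plan does not choose between them.

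**The case against.** The strongest reply is that this is a permission, not a practice. The clause says that participants may be removed, nothing forbids assessing them afterwards, and the statistical section does not say that incomplete cases are dropped. That is fair: both the lack of follow-up and the default to available data are inferred from silence. What stands is that removal is expressly from the study, that no later visit is described, and that the named tests have no rule for absent values.

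Several stronger readings are tempting and are not supported:

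- **That the bias favours the device.** Controls might need other treatment more often, which would push the other way. All arms wear the sleeve and follow the same exercise and walking programme, so much of the burden is shared.
- **That removal of 30% versus 0% is the expected case.** No section gives a removal rate or an arm difference. It is the extreme row of the table, and the equal row gives zero.
- **That the plan expects only 32 of 45 to finish.** It says the number was raised to allow for dropouts.
- **That those removed for other treatment have the worst knee pain.** The clause is not limited to the knee and could cover any condition.
- **That adherence is always inflated.** Usage before removal is already logged. The mean is overstated if removed participants are excluded. If they are kept on a full-schedule denominator, removal lowers it.

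**Conclusion.** The point holds as a design weakness that should be corrected. The protocol does not separate stopping the programme from stopping data collection. It allows removal on grounds that overlap a secondary outcome and may overlap primary ones, and it has no analysis set, missing-data method or adherence denominator to limit the consequences.

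The documents determine neither the size nor the direction of the bias. Under the assumed normal model with r = 0.3 to 0.7, it runs from 0 SD between arms (equal removal, equal r) through 0.09 to 0.21 SD (30% versus 10%) to 0.15 to 0.35 SD in the extreme case of 30% versus 0%. Within-arm tests shift whether or not removal is balanced. These figures show that moderate, uneven removal could matter next to an effect of 0.71. They do not predict that it will happen.

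**What to change.** 1. **Study Withdrawal.** State that stopping the device or programme, for whatever reason, does not by itself end study participation, and that non-compliance is not a ground for ending data collection. Participants who stop are still invited to the existing week-6 and week-12 assessments unless they withdraw consent or the investigator judges an assessment unsuitable for them. Clinical decisions to stop treatment are unchanged.
2. **Data Analysis/Statistical Analysis.** State that all randomised participants are analysed in their assigned arm. Name the method for values still missing, and add a sensitivity analysis in which the missing values depend on outcome.
3. **Adherence to Program.** Compute adherence for every randomised participant over the full prescribed schedule (60 exercise and 36 walking sessions, in the repetitions and minutes prescribed), counting zero after stopping.
4. **Medication.** Type and dosage are already collected, but the timing is not stated. Record them at each visit so that added treatment can be described by arm.
5. **Compensation for Participation.** Say whether someone who stopped the programme but attended the visits counts as having completed the study.

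The cost is protocol and SAP wording, plus attendance at visits already in the schedule by people who would otherwise have left. The downside is that the estimated effect will include people who stopped, so it may be smaller.
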